5.2 Analysis methodology

Statistical analysis will be performed using R Software. Categorical variables will be compared between cells and groups using Chi-square or Fisher's exact test. Continuous data distribution will be assessed using Shapiro Wilk test. According to the results of the normality test, between groups differences will be assessed by the proper Student's t test (paired or unpaired) or the equivalent non-parametric test (Wilcoxon, Mann-Whitney). Two-way ANOVA or general linear regression models will be used to assess the effect of two or more variable of the study outcomes. P-values <0.05 will be considered statistically significant.

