5.0 Statistical methodology

5.1 Sample size

The sample size was calculated considering as primary outcome the proportion of patients not responder to treatment (according to OMERACT-OARSI [1] criteria) at the 12-month follow-up in two distinct groups of patients: subjects with body mass index within the reference ranges (Group 1 and 3) and subjects with values outside the range (Group 2 and 4). The proportion of unresponsive patients is expected to be 0.45 in Group 1 and 0.05 in Group 2. Considering a power of 80% and a significance level of 0.05 for a one-tailed Fisher exact test, the sample size is 20 subjects per group and considering 10% of possible dropouts, this number is increased to 22 patients. The study will be replicated in two classes of patients, undergoing PRP or microfragmented adipose tissue treatments. Then, 44 patients will be enrolled per class, for a total of 88 patients.

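### The protocol sizes the responder contrast on a one-tailed Fisher test but leaves its analysis to Chi-square or Fisher with no sidedness; naming Boschloo's exact test removes the choice and adds about 4 to 7 points of power

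*Protocol*

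**What the plan says.** Protocol section 5.1 plans the comparison of non-responder proportions between BMI groups as follows: "Considering a power of 80% and a significance level of 0.05 for a one-tailed Fisher exact test". The assumed rates are: "The proportion of unresponsive patients is expected to be 0.45 in Group 1 and 0.05 in Group 2". The resulting size is: "the sample size is 20 subjects per group and considering 10% of possible dropouts, this number is increased to 22 patients". The comparison is made separately for PRP and for microfragmented adipose tissue, so "44 patients will be enrolled per class, for a total of 88 patients".

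Section 5.2, repeated in the statistical analysis row of the Synopsis, gives one general sentence for all categorical variables: "Categorical variables will be compared between cells and groups using Chi-square or Fisher's exact test". The threshold is "P-values <0.05 will be considered statistically significant". Neither place says which of the two tests applies to responder status, whether it is one- or two-sided, or whether Chi-square carries a continuity correction.

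**The concern.** Responder status is yes/no, and each BMI contrast rests on about 20 against 20 patients. At that size Fisher's test, which conditions on both margins, can use only about half of its nominal 5%, while uncorrected Chi-square slightly exceeds it. Two things are at stake:

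- **Discretion.** Section 5.1 ties the contrast to one test and one sidedness; section 5.2 does not carry either forward. The same table can be called significant or not, depending on which permitted reading the analyst takes.
- **Efficiency.** Enrolment is fixed, so error allowance that the test cannot spend is power forgone. An unconditional exact test recovers part of it from the same patients.

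**Working it through.** **Inputs (protocol 5.1 and 5.2).** 20 evaluable per BMI group within a treatment class; non-responder rates 0.45 and 0.05; level 0.05; planned power 80%; one-tailed Fisher in 5.1; Chi-square or Fisher, sidedness unstated, in 5.2.

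**Method.** List all 21 × 21 outcomes (a, b), where a and b are the non-responders among 20 in each group. For a given test,

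P(reject) = Σₐ Σ_b Bin(a; 20, p₁) · Bin(b; 20, p₂) · 1[test rejects at (a, b)].

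Power uses p₁ = 0.45 and p₂ = 0.05. Maximum size is the largest value over a common rate p₁ = p₂.

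**The plan's own figure.** With two-sided Fisher, power is 78.9% at 19 per group and 81.8% at 20, so 20 is the smallest two-sided size for 80%. With the stated one-tailed Fisher, 17 per group already gives 81.1%, and 20 gives 89.0%. The target is met on either basis, but the number labelled one-tailed is the two-sided one. This is a further reason to settle sidedness.

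**The options at 20 vs 20.**

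| Test | Maximum size | Power at 0.45 vs 0.05 |
|---|---|---|
| Fisher, one-sided | 2.7% | 89.0% |
| Fisher, two-sided | 2.5% | 81.8% |
| Chi-square, corrected, two-sided | 2.2% | 80.4% |
| Chi-square, uncorrected, two-sided | 5.3% | 89.5% |
| Boschloo, one-sided | 4.3% | 92.8% |
| Boschloo, two-sided | 4.6% | 88.8% |

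Boschloo's test orders tables by their Fisher P-value and sets the cut-off so that the maximum size stays at or below 5%. Two-sided, it rejects when Fisher's P is at most 0.0915. Every table that Fisher rejects is therefore also rejected.

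**One table, different verdicts.** Take 8/20 vs 2/20 non-responders:

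- Uncorrected Chi-square: 40 × (8×18 − 2×12)² / (20×20×10×30) = 40 × 120² / 120,000 = 4.80, P = 0.028.
- Corrected Chi-square: 40 × (120 − 20)² / 120,000 = 3.33, P = 0.068.
- Fisher: two-sided P = 0.065, one-sided P = 0.032.

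All four readings are compatible with 5.2; two are below 0.05 and two are not. Summed over all tables, uncorrected Chi-square is significant while two-sided Fisher is not in 7.7% of studies at the planned rates.

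**Gain from Boschloo at the planned rates.** One-sided: 92.8 − 89.0 = 3.8 points. Two-sided: 88.8 − 81.8 = 7.0 points. If all 22 enrolled per group were evaluable, the gains would be 96.0 − 92.2 = about 4 points one-sided and 92.2 − 86.5 = about 6 points two-sided.

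**Gain at smaller differences (assumed rates, not in the protocol).**

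| Rates | One-sided, Fisher to Boschloo | Two-sided, Fisher to Boschloo |
|---|---|---|
| 0.45 vs 0.10 | 74.1% to 81.2% (7 points) | 62.4% to 72.6% (10 points) |
| 0.45 vs 0.15 | 57.2% to 65.6% (8 points) | 44.3% to 54.3% (10 points) |

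**The case against.** The strongest reply is that nothing here is invalid. Fisher holds its level, the study was sized on it, and its conservatism is already paid for in the 20 per group. The planned 80% power is met one- or two-sided. Preferring an unconditional to a conditional exact test is a methodological choice. That stands, and it limits the point to an improvement.

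It can also be said that the sentence in 5.2 is generic, that 5.1 names Fisher for this contrast, and that choosing between two standard tests is often left to a statistical analysis plan, which is not at hand. This stands in part. Read together, the sections do give the contrast a planning test. But the protocol itself states a test and a sidedness in 5.1 and then allows more than that in 5.2, so the looseness is in the text shown.

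Uncorrected Chi-square, which 5.2 permits, already has 89.5% two-sided power. True, but its maximum size is 5.3%, whereas Boschloo reaches nearly the same power within 5%.

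Finally, sidedness matters as much as the choice of test: one- against two-sided Fisher is 89.0 − 81.8 = 7.2 points at the planned rates. This is correct, and naming a test without its sidedness would leave that ambiguity open.

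**Conclusion.** The point holds as a worthwhile, low-cost improvement. Sections 5.1 and 5.2 need to agree on one test and one sidedness for the responder contrast. Boschloo's test is the better choice at this sample size, worth about 4 points of power one-sided or 7 points two-sided at the planned rates.

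Three stronger readings might be inferred, and the documents do not support them:

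- **That Fisher makes the analysis invalid or the study underpowered.** It does neither at the stated rates.
- **That Fisher costs 7 to 10 points in general.** That range is two-sided only, and the 10 needs a smaller difference than the protocol assumes. On the stated basis, "a significance level of 0.05 for a one-tailed Fisher exact test", the gain at the planned rates is 3.8 points.
- **That one patient would decide which test is used, because the expected cell count at the planned rates is exactly 5.** At 9/20 and 1/20 it is 20 × 10/40 = 5, but switching tests at that count is an outside custom and the protocol contains no such rule.

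The figures assume 20 evaluable patients per group, independent responses, and separate analysis of each treatment class.

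**What to change.** In section 5.2 and the Synopsis, take the comparison of responder proportions between BMI groups out of the general sentence on categorical variables. Name Boschloo's unconditional exact test at 0.05 as its single test, applied within each treatment class. State whether it is one- or two-sided, and the direction if one-sided, and make section 5.1 and the sample size row of the Synopsis agree. Report an exact confidence interval for the difference in proportions. Any Fisher P-value shown alongside is descriptive and does not decide significance. Keep enrolment as planned.

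The cost is a sentence or two in each place and an R package; R is already the stated software. No extra patients, visits or data are needed. The downside is a test that some readers will know less well than Fisher's.

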6.0 Potential risks/benefit

6.1 Benefits

Patients will not have direct benefits by participating in this study. Compared to the enlarged scientific community, the study may indirectly contribute to an extension of knowledge in the direction of potential clinical applications of the results obtained.

The identification of new associations between the evaluation of nutritional status (including anthropometric measurements of body composition, biochemical analysis, evaluation of food consumption and energy expenditure), quality of orthobiologics and clinical outcome of patients will allow to predict which or how nutritional aspects has an impact on clinical result. In this scenario, the results of this study will allow to identify the need of possible modification of patients' food habits to favor better results of the regenerative treatment, improving their life quality and reducing the societal economic burden.

6.2 Potential risks

One risk could be related to blood sampling for biochemical assays: possible complications could be lipotimia, slight pain or irritation at the sampling site. Another risk could be related to the detection of anthropometric measurements such as redness at the landmark with skinfolder.

7.0 Ethical Considerations

The protocol is compliant with current Declaration of Helsinki, with EN ISO 14155: 1 and EN ISO 14155: 2 and the Good Clinical Practice (GCP) and all the staff involved in the study is committed to acting in accordance with the principles contained therein.

7.1 Ethics Committee

All documentation relating to this study must be submitted to the Ethics Committee, for the necessary approvals. The beginning of the study and the inclusion of individuals is subordinate to the favorable opinion expressed by Ethics Committee.

Any amendment to the protocol, information to the patient and the informed consent form must be submitted to the Ethics Committee.

It is the responsibility of the principal investigator of the study to inform the ethics committee of complications or adverse events that may be of interest to the subjects included in the study and any problems that may present a risk to the subject, according to current regulations.

7.2 Subject information and informed consent

Before being included in the study, subjects who meet all the criteria for inclusion and exclusion of the study, should be informed in detail by persons authorized by the principal investigator and be placed in a position to understand objective, meaning, duration of the study. All the risks / benefits, advantages / disadvantages must be discussed with the subject. Before admission to the study, the subject must give their written informed consent by signing and dating the form, of which will receive a copy. The subject is guaranteed that participation in the study is voluntary and that at any moment can withdraw from the study without suffering any consequences.

7.3 Insurance and monitoring

The only additional procedure that implies a minimal risk is blood sample collection. Then, the Sponsor assume that a specific insurance policy is not necessary. For the same reason no monitoring activities will be performed.

7.4 Protection of personal data

The researcher conforms to the principle of the right of the subject to the protection of privacy under Legislative Decree no. 196/2003 and ssm and UE regulation 679/2016 and guidelines of the privacy authority 24/07/2008. All clinical data recorded on the CRF and used for further evaluation are anonymous. Patient's clinical data and are coded by number of subject, date of birth and identification is restricted to authorized personnel involved in the study and under the responsibility of the researcher. Clinical data of the subject are stored and processed electronically for purposes of scientific evaluation, but any discussion or analysis of the data will always be done anonymously.

8.0 Administrative Procedures

8.1 Curriculum vitae

The PI of the project can provide an updated CV demonstrating her experience in research projects in the field of nutrition and regenerative medicine for musculoskeletal disorders. She has a special research interest in the characterization of orthobiologics products such as PRP and microfragmented adipose tissue. In particular, she has been involved in several in vitro and clinical studies including the investigation of the importance of the nutritional

role in post-operative recovery of orthopaedic patients, as well as the role of mesenchymal stem cells and tissue resident progenitor cells for the treatment of musculoskeletal disorders.

8.2 Information about Staff involved

The researcher has the responsibility to inform all personnel involved in the study of all the relevant aspects of the study. A list of personnel designated by the principal investigator to be involved directly or indirectly in the study in question should be set up, updated and stored.

8.3 Publications

All data collected in this study are property of the IRCCS Galeazzi Orthopaedic Institute.

It is foreseeable the production of manuscripts and abstract. The principal investigator is committed to the publication of results and will be responsible for publishing the results of this study. The principal researcher can publish or present the study results in accordance with this section of the protocol.

The principal investigator is entitled to use the results of all the work produced according to this protocol, including, but not limited to, test results and statistical data obtained. The principal institute/researcher agrees that, apart from his or her employees, executives, collaborators, and representatives, the data will not be disclosed except after written consent.

It is the responsibility of the principal investigator to send the study report to the competent authorities.

8.4 Funds

Funds for lab analysis and for preliminary activities of the Ethical Committee will be covered with funds of the Ministry of Health and research funds.

